10 STUDY CALENDAR

Baseline evaluations (vital signs, physical exam, ECOG performance status) are to be conducted within 2 weeks prior to start of protocol therapy. Informed consent, tumor assessment by imaging, laboratory evaluation, echocardiogram, and EKG must be done \leq 4 weeks prior to the start of therapy. If the participant's condition is deteriorating, laboratory evaluations should be repeated within 48 hours prior to initiation of the next cycle of therapy. Assessments must be performed prior to administration of any study agent. Study assessments and agents should be administered within \pm 3 days of the protocol-specified date, unless otherwise noted.

	Screening*	Day 1 of each cycle of chemotherapy**	RT***	Surgery ****	Off Tx*****	Post Tx Follow-up*****	EDC Timepoints
FOLFIRINOX ^{A,B}		X					
NIS793 ^{C,D}		X					
Fluorouracil ^E			X				
Informed Consent	X						N/A
Tests & Observations							
Medical History	X						N/A
Concurrent Medications ^a	X						N/A
Physical Exam ^b , Vital Signs ^c	X	X	X	X	X	X	N/A
Height	X						N/A
ECOG Performance Status	X	X	X	X	X	X	Prior to registration, Day 1 of every cycle, prior to radiation, surgery, Off treatment
Adverse Event Assessment [†]		X	X	X	X	X	All visits
Laboratory Studies							
CBC, Differential, Platelets ^{d,f}	X	X	X	X	X	X	N/A
Serum Chemistry ^{e,f}	X	X	X	X	X	X	N/A
HIV, Hepatitis B/C serologies	X						
Pregnancy Test	X	X ^r					N/A
CA 19-9, CEA ^g	X	X	X	X	X	X	N/A
EKG ^h	X	X					N/A
Troponin I, NT proBNP ⁱ	X	X					N/A
Echocardiogram or MUGA or cardiac CT/MRI ^j	X						Prior to registration. Thereafter only if clinically indicated &/or if cardiac enzymes are elevated
Tumor Measurements ^k	X		X	X		X	Prior to registration, every 8 weeks on chemotherapy, prior to radiation, prior to surgery
Pathology Review ^{l,m}				X			
Optional tumor biopsy ⁿ	X				X		Prior to registration at baseline and at time of progression.
Archival tumor sample ^o	X						Prior to registration at baseline.
Research blood ^p	X	X	X	X ^q	X	X	Prior to registration, Day 1 of all chemotherapy, Prior to radiation, prior to surgery, off treatment

A: Fluorouracil 2400mg/m² IV on days 1 over 46 hours; Leucovorin 400mg/m² on day 1; Irinotecan 150mg/m² IV on day 1; Oxaliplatin 85mg/m² IV on day 1 of a 14 day cycle (+3/-1 days) for patients randomized to Arm A and B (See section 5.1).

B: Subcutaneous growth factor support will be administered between 0 and 72 hours after discontinuation of continuous infusion of 5-FU in all patients receiving FOLFIRINOX after each cycle. Participants may self-administer at home or have the injection administered in clinic.

C: NIS793 2100mg IV on day 1 of a 14-day cycle (+3/-1 days) for patients randomized to Arm A (See section 5.3)

D: The first five patients randomized to NIS793 (Arm A) will be part of a safety lead-in. Study will pause until the last patient accrued for safety lead-in has completed two full treatment cycles (i.e., 28 days). Participants must have received at least 75% of their assigned doses of FOLFIRINOX and NIS793 to be considered evaluable for this safety analysis, unless dosing was held or reduced due to toxicity. If one or more of the first five participants enrolled does not meet this parameter for a reason other than toxicity (e.g. rapid disease progression and subsequent removal), Arm A will continue to accrue as many participants as needed to have five evaluable participants for safety assessment.

E: Capecitabine twice daily on days of radiation OR Fluorouracil by continuous infusion on days of radiation. Doses to be determined by institutional standards and physician discretion but the recommended doses are 5FU 225mg/m²/day continuous infusion Monday-Friday, Capecitabine 1650mg/m²/day po.

* Screening evaluation (vital signs, physical exam, ECOG performance status) are to be conducted within 2 weeks of starting protocol therapy. Informed consent, tumor assessment by imaging, laboratory evaluation, echocardiogram, and EKG must be done <= 4 weeks prior to start of therapy.

** Drug dosages to be modified due to changes in body weight or body surface area (BSA) based on institutional criteria. If no such criteria exist recalculate doses when there is a greater than 10% change in weight or BSA.

*** RT only delivered for patients with borderline resectable PDAC. Radiation planning visit should occur at the time of Cycle 7 of treatment. Assessments should be done approximately weekly, and at least once for every five fractions of radiation.

**** Surgical assessments should be done once within 14 days prior to the operation.

***** End of treatment appointment to be performed within 4 weeks of the last study treatment event. Performed prior to the initiation of any non-study related cancer therapies.

***** Post treatment follow up should be at least once every 12 weeks (+/- 28 days) until first disease progression event, new regimen of anti-neoplastic therapy, or until death, whichever occurs first. Participants removed from protocol therapy for unacceptable adverse event(s) will be followed until resolution or stabilization of the adverse event.

^a If new medications or changes are prescribed while patient is receiving treatment on study, these medications should be recorded.

^b A complete physical examination will be performed at baseline, prior to radiation and prior to surgery. A limited physical exam will be completed prior to therapy on Day 1 of the 8 cycles of chemotherapy +/- NIS793, and weekly during chemotherapy and radiation.

^c Vital sign assessments include measurements of heart rate, systolic and diastolic blood pressures, respiratory rate, temperature, and weight.

^d Hematology includes: hemoglobin, hematocrit, platelet count, RBC count, WBC count, and percent and absolute differential count. Results must be available prior to the administration of study drug. ANC must be ≥ 1500 for eligibility and Cycle 1 Day 1. Subsequent ANC must be ≥ 1000 .

^e Albumin, alkaline phosphatase, total bilirubin, bicarbonate, BUN, calcium, chloride, creatinine, glucose, LDH, phosphorus, potassium, total protein, SGOT [AST], SGPT [ALT], sodium.

^f Labs completed prior to registration may be used for day 1 of cycle 1 if obtained ≤ 7 days prior to treatment (except pregnancy test, CA 19-9, cea). Labs (hematology and serum chemistry) to be drawn every 2 weeks during chemotherapy, weekly during radiation, prior to surgery (+/- 2 weeks), and 2 weeks with the post-operative assessment.

^g Ca19-9 and CEA to be checked during screening, day 1 of all cycles of chemotherapy, prior to chemotherapy and radiation (+/- 2 weeks), prior to surgery (+/- 2 weeks), and at post-treatment follow up.

^h EKG will be performed at screening for all patients. Thereafter EKG is required on day 1 of each cycle of chemotherapy for *patients receiving NIS793*. QTc to be calculated using Bazzett's formula.

ⁱ Cardiac specific enzyme Troponin I and NT-proBNP will be checked on screening for all

patient and thereafter will be checked on C3D1 and day 1 of every third cycle during treatment duration or as clinically indicated, and at EOT visit for the patients randomized to the NIS793 arm.

^j Echocardiogram or other cardiac imaging such as MUGA or CT or MRI should be done in *patients receiving NIS793* prior to cycle 1. Thereafter it is repeated only if clinically indicated &/or if cardiac enzymes are elevated: $\geq 2x$ ULN (if normal at screening) or $\geq 2x$ baseline (if baseline value was elevated).

^k Tumor assessments should consist of 1) CT chest/abdomen/pelvis and/or MRI of the abdomen/pelvis, and 2) any other imaging studies (CT neck, plain films, etc.) as clinically indicated by the treating physician. The same radiographic procedures and technique must be used throughout the study for each patient (e.g., if the patient had CT chest/abdomen/pelvis performed during screening, then she should subsequently undergo CT performed using the same radiologic protocol throughout the remainder of the study). In case of CT abdomen/pelvis is used as the radiographic modality it should be protocolled specifically for evaluation of pancreas i.e. Pancreas protocol CT. Tumor assessments will be \pm 4 weeks prior to C1D1, every 8 weeks during chemotherapy (\pm 2 weeks), then once (\pm 2 weeks) prior to start of radiation, and once (\pm 2 weeks) prior to surgical date, then and once every 12 weeks (\pm 28 days) after surgery. Additional scans are permitted as clinically indicated.

^l In cases where surgery is aborted due to intra-operative identification of unresectable or metastatic disease a tissue biopsy of the primary pancreatic tumor should be performed as long as deemed safe by the primary surgeon.

^m Patients with imaging evidence of disease progression precluding surgery at restaging imaging will be offered an optional percutaneous or endoscopic biopsy of primary pancreatic tumor.

ⁿ Patients will be consented for an optional tissue biopsy of the primary pancreatic tumor during initial consenting process.

^o Archive tissue biopsy from diagnostic specimen would be obtained.

^p Research blood collection. See lab manual.

^q Research blood to be collected within 14 days prior to the operation.

^r In female subjects of child-bearing potential as defined in the eligibility criteria, pregnancy test must be performed within 24 hours prior to the initial administration of study drug, then every 4 weeks \pm 1 week.

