1.3 Secondary Objectives

- 1.3.1 To evaluate the safety and tolerability of the investigational agent NIS793, a TGF-beta inhibitor, in combination with mFOLFIRINOX, in patients with resectable or borderline resectable pancreatic adenocarcinoma.
- 1.3.2 To evaluate the progression-free survival (PFS) and overall survival (OS) of the investigational agent NIS793, a TGF-beta inhibitor, in combination with mFOLFIRINOX, in patients with resectable or borderline resectable pancreatic adenocarcinoma.

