7.1.2 Adverse Event List(s) for mFOLFIRINOX (Fluorouracil, leucovorin, oxaliplatin, irinotecan)

7.1.2.1 5-Fluorouracil:

Very Common (more than 1 in 10 patients)

- Sickness
- Vomiting
- Mouth sores
- Diarrhea
- Abdominal pain
- Tiredness
- Swelling and redness of the skin
- Fever

Less Common (less than 5 in 100)

- Itching, peeling, and/or pain of the skin of the hands and feet (hand-foot syndrome)
- Diminished appetite
- Loss of hair
- Dizziness
- Cardiac disorders such as angina
- Heart attack and change of heart rhythm
- Confusion
- Disorientation
- Emotional instability
- Watering of the eyes due to excessive tear production
- Abnormal drowsiness
- Weakness
- The lowering of blood cells
- Bleeding or bruising

7.1.2.2 Leucovorin:

Less Common (less than 5 in 100 patients)

- Allergic reaction
- Rash
- Itching
- Facial flushing

- Nausea
- Vomiting

7.1.2.3 Irinotecan:

Very Common (more than 1 in 10 patients)

- A decrease in blood counts (red blood cells, white blood cells, and platelets)
- Anorexia
- Mild Diarrhea
- Mild fatigue
- Sores in the mouth and throat (mucositis)
- Cardiovascular events such as a fast or irregular heartbeat
- Hair loss
- Abnormal liver test values
- Decreased kidney function
- Nausea and vomiting
- Constipation
- Pain

Less Common (less than 5 in 100 patients)

- Severe Diarrhea
- Hemorrhage which may require a blood transfusion
- Moderate fatigue
- Infection

Rare but Serious

- A serious decrease in blood counts that could result in infection, sepsis, a need for blood transfusion, a need for platelet replenishment
- Liver failure that may lead to death
- Kidney failure that may lead to death or the need for dialysis
- Heart attack
- Stroke

- Hypertension

7.1.2.3 Oxaliplatin:

Very Common (more than 1 in 10 patients)

- Peripheral sensory neuropathy, especially in the case of cold exposure, and an unusual feeling of numbness of the mouth and throat that may cause difficulty in swallowing, and can be made worse by cold water or drinks
- This neuropathy can cause the following:

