13.7 Reporting and Exclusions

13.7.1 Evaluation of Toxicity

All patients will be evaluable for toxicity from the first dose of protocol therapy.

For patient safety, a Bayesian toxicity monitoring rule will be implemented for the dose limiting toxicity (DLT) events that are at least possibly related to the investigational agent in the opinion of the investigators and occur within 28 days from the end of the drug administration according to Common Terminology Criteria for Adverse Events (CTCAE) v5.0. DLT events will include:

- Grade 3 or higher non-hematologic toxicity except:
 - Grade 3 fatigue
 - Grade 3 diarrhea or vomiting that lasts less than 72 hours
- Grade 4 or higher hematologic toxicity and:
 - Febrile neutropenia
 - Grade 4 neutropenia lasting longer than 7 days

Let p_{tox} be the toxicity probability at least possibly related to the investigational agent in the opinion of the investigators with a prior distribution of $\text{Beta}(0.33, 0.67)$, then if $\text{Pr} [p_{\text{tox}} > 0.33] > 0.7$, we will terminate the experimental arm early. Patients within the safety lead in cohort of the first 5 patients will be monitored for DLT at least possibly related to investigational agent. Based on these assumptions and monitoring conditions, we will early stop the study if we observe $[\# \text{ patients experiencing toxicity}] / [\# \text{patients being treated}] \geq 3/5$ DLTs in the safety lead in cohort. The operating characteristics are shown in Table 2.

Table 2. Operating characteristics for toxicity monitoring

True toxicity probability	Early stopping probability	Average sample size
0.1	0.010	29.8
0.2	0.093	28.0
0.3	0.354	23.4
0.4	0.710	16.7
0.5	0.931	11.0

The toxicity boundaries and operating characteristics were generated using web-based applications available at <https://trialdesign.org>.

Safety data analysis: Toxicity severity and grade data will be summarized with descriptive statistics overall and by treatment arms.

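### Scheduled on-treatment EKGs, and most naturally cardiac enzymes, fall only in the NIS793 arm, so silent cardiac findings are likely to look more frequent there in the by-arm toxicity summary

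*Combined protocol and SAP*

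**What the plan says.** Section 10, footnote h, starts both arms equally: "EKG will be performed at screening for all patients". It then separates them: "Thereafter EKG is required on day 1 of each cycle of chemotherapy for" patients receiving NIS793.

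Footnote i checks troponin I and NT-proBNP in everyone at screening. The enzymes "thereafter will be checked on C3D1 and day 1 of every third cycle during treatment duration", or when clinically indicated, "and at EOT visit for the patients randomized to the NIS793 arm".

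Footnote j covers echocardiography or other cardiac imaging after the start of treatment: "Thereafter it is repeated only if clinically indicated &/or if cardiac enzymes are elevated".

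No section schedules any of these tests in Arm B after screening.

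On the analysis side, Section 1.3 has a secondary objective: "To evaluate the safety and tolerability of the investigational agent NIS793, a TGF-beta inhibitor, in combination with mFOLFIRINOX". The safety analysis in Section 13.7.1 is one sentence: "Toxicity severity and grade data will be summarized with descriptive statistics overall and by treatment arms". It does not mention that the arms are tested on different schedules.

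**The concern.** A silent QTc prolongation or troponin rise becomes an adverse event only if someone runs the test. Arm A is tested on a schedule. Arm B is tested only when a clinician has a reason. A by-arm table of such findings then mixes any drug effect with the difference in looking.

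The class matters to readers of this trial. Section 7.1.1 lists cardiac toxicity for NIS793, and Section 6.2 has graded rules for QTc prolongation and cardiac enzyme elevation. Section 2.2 says that NIS793 had not yet been combined with FOLFIRINOX in clinical trials. The 15 Arm B patients are therefore the trial's only concurrent reference for what mFOLFIRINOX produces by itself. An excess of silent findings in Arm A could be read as a NIS793 signal when it partly reflects the testing schedule.

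**Working it through.** The plan gives no figure for this point, so there is none to reproduce. The check has four steps.

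**1. Count the scheduled tests.** Both arms have 8 cycles (Section 5.3.2).
- EKG, Arm A: day 1 of cycles 1 to 8, which is 8 readings. Section 10 requires assessments before any study agent is given, and Section 6 collects adverse events from the first dose. The cycle 1 day 1 EKG is therefore a pre-dose reading, which leaves 8 − 1 = 7 that can reveal an on-treatment event.
- Enzymes, Arm A: cycle 3, cycle 6 and end of treatment, which is 3 panels.
- Arm B: 0 scheduled EKGs and 0 scheduled enzyme panels after screening.
- If all 30 Arm A patients complete treatment: 30 × 7 = 210 informative EKGs and 30 × 3 = 90 enzyme panels, against 0 and 0.
- Imaging under footnote j follows elevated enzymes, so the imbalance carries over to imaging findings.

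**2. Follow the findings to the table.** Section 7.3.4 has all adverse events captured and reported to the sponsor-investigator, and Section 13.7.1 summarizes them by arm. The calendar gives the data-capture timepoints for EKG and enzymes as N/A. The abnormalities therefore appear to reach the tables through adverse event reports, with no planned record of whether a scheduled test found them.

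**3. Illustrate with no drug effect.** Let p be the chance that one EKG reading shows an incidental abnormality. The documents do not give p; 1%, 2% and 5% are assumptions, as is independence between readings. The chance of at least one finding in 7 readings is 1 − (1 − p)^7.

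| p | 1 − (1 − p)^7 | × 30 in Arm A | Found by schedule in Arm B (15) |
|---|---|---|---|
| 0.01 | 1 − 0.9321 = 6.8% | 2.04 | 0 |
| 0.02 | 1 − 0.8681 = 13.2% | 3.96 | 0 |
| 0.05 | 1 − 0.6983 = 30.2% | 9.05 | 0 |

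Repeat EKGs in one patient are likely to be correlated, which would lower these percentages.

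**4. Allow Arm B some detection.** Give both arms the same true rate of silent findings. Let Arm A detect all of them and Arm B a fraction d. With exact binomial counts for 30 and 15 patients, the probability that Arm A shows the higher observed rate is:

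| True rate (assumed) | d = 0 | d = 25% | d = 50% | d = 100% |
|---|---|---|---|---|
| 10% | 0.96 | 0.82 | 0.68 | 0.45 |
| 20% | 0.999 | 0.93 | 0.79 | 0.46 |
| 30% | 1.00 | 0.97 | 0.86 | 0.46 |

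The last column is equal testing; it lies below one half because ties are possible. At a true rate of 20% and d = 50%, the expected counts are 30 × 0.20 = 6.0 in Arm A and 15 × 0.20 × 0.50 = 1.5 in Arm B, so the observed rates are 20% and 10% with no drug effect.

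**The case against.** Closer cardiac monitoring of the investigational arm is defensible when the agent has a listed cardiac risk. The case against making more of it is strong on several points, and these stand:

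- **Only part of the cardiac class is affected.** A reader might infer that all cardiac findings will look like a NIS793 effect because controls are not tested. The documents do not support that. Arm B has a screening EKG and enzymes, can be tested when clinically indicated, and has adverse event assessment at every visit. Vital signs, including heart rate and blood pressure, are scheduled for both arms.
- **The chemotherapy lists do not supply the missing rate.** A reader might take the irinotecan entry in Section 7.1.2, "Cardiovascular events such as a fast or irregular heartbeat", together with the 5-FU cardiac entries, as proof of a background rate of silent abnormalities. Those entries are mostly events that cause symptoms or can show in heart rate. The lists for the mFOLFIRINOX drugs name neither QTc prolongation nor enzyme elevation. Section 3.2 also excludes patients with significant cardiac disease.
- **The enzyme restriction is less certain than the EKG one.** In footnote i the closing words about the NIS793 arm could grammatically attach to the end-of-treatment visit alone, and the calendar grid marks day 1 without naming an arm. Applying them to the whole on-treatment schedule is the natural reading but not the only one. Footnote h has no such ambiguity.
- **An abnormal EKG is not automatically a graded adverse event.** The counts in the working are not forecasts of table entries.
- **No decision rests on the comparison.** The safety objective describes the combination, the summary is descriptive with no test, and each event carries an attribution.

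None of this removes the point. Nothing in the plan tells a reader of the by-arm table that silent cardiac findings were searched for on a schedule in one arm only.

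**Conclusion.** The concern holds for silent, test-defined findings: QTc prolongation, enzyme rises, and imaging findings that they trigger. As the plan is written, these are likely to appear more often in Arm A in the Section 13.7.1 summary even if NIS793 has no cardiac effect.

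The size cannot be fixed from the documents. The range of about 2 to 9 of 30 Arm A patients rests on assumed, independent abnormality rates of 1% to 5% per reading and on full completion of 8 cycles. The EKG part rests on footnote h, which is clear; the enzyme and imaging part rests on the natural reading of footnote i.

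A reader might also infer that the toxicity stopping rule is distorted. It is not distorted by this imbalance: the rule in Section 13.7.1 monitors the experimental arm alone and compares nothing with Arm B. The consequence is limited to how a descriptive safety table is read, so this is a cheap improvement to the analysis plan rather than a flaw in a trial decision.

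**What to change.** Change Section 13.7.1 and the adverse event form:

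1. Add a field to the adverse event form recording whether a cardiac finding came from a scheduled protocol test, from imaging triggered by such a test, or from symptoms or a clinically indicated test. Collect it prospectively, because the detection source may not be recoverable later.
2. Report findings from scheduled tests, and from imaging that those tests triggered, in a separate Arm A table that is not set against Arm B.
3. In the by-arm cardiac summary, compare only symptomatic or clinically indicated findings, with a note that the arms were tested on different schedules.

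Also reword footnote i so that the arm to which the on-treatment enzyme schedule applies is explicit.

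The cost is one form field, one table specification and a footnote. Monitoring in Arm A is unchanged and no test is added. There are two downsides. The comparative table will hold fewer events. Some bias will also remain: treatment is open-label, so the decision to test on clinical grounds may differ by arm, and scheduled Arm A tests may pre-empt clinically indicated ones or lead to holds that prevent later symptomatic events. The note in step 3 should say so.

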5.2. Pre-Treatment Criteria

Cycle 1, Day 1, and Subsequent Cycles:

- History and physical exam with vital signs, body weight, and height (obtained within 2 weeks (14 days)).

Laboratories will be collected as follows:

- Hematological profile: CBC with differential on day 1 of each cycle
- Complete metabolic profile: Electrolytes, BUN, creatinine, liver function tests (albumin, total protein, AST, ALT, alkaline phosphatase, total bilirubin), and magnesium on day 1 of each cycle
- Tumor marker profile: CA 19-9 and CEA on day 1 of each cycle
- ANC must be ≥ 1500 for eligibility and Cycle 1 Day 1. Subsequent ANC must be ≥ 1000 .

*For all laboratory measures a window of up to 3 days prior to treatment day is acceptable.

*Baseline laboratory values obtained on Day 1 Cycle 1, with the exception of ANC as noted above, will not affect the patient's eligibility to participate in the study after the patient has undergone successful screening and randomization.

*Results must be available prior to the administration of study drug.

Imaging studies will be performed as follows:

- Chest/Abdomen/Pelvis CT scan or Chest CT scan and Abdomen/Pelvis MRI must be performed within 28 days of the date of registration. In case of CT abdomen/pelvis is used as the radiographic modality it should be protocolled specifically for evaluation of pancreas i.e. Pancreas protocol CT.

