Eligible patients with newly diagnosed resectable or borderline resectable pancreatic adenocarcinoma will be randomly assigned in a 2:1 allocation ratio to one of the two interventions: NIS793 and FOLFIRINOX chemotherapy for 8 cycles (Arm A, Experimental arm) followed by surgery, or FOLFIRINOX for 8 cycles (Arm B, Control arm) followed by surgery. The experimental (Arm A) and control arms (Arm B) will accrue 30 and 15 patients respectively. The first five patients randomized to NIS793 (Arm A) will be part of a safety lead-in. Study will pause until the last patient accrued for safety lead-in has completed two full treatment cycles (i.e., 28 days). Participants must have received at least 75% of their assigned doses of FOLFIRINOX and NIS793 to be considered evaluable for this safety analysis, unless dosing was held or reduced due to toxicity. If one or more of the first five participants enrolled does not meet this parameter for a reason other than toxicity (e.g. rapid disease progression and subsequent removal), Arm A will continue to accrue as many participants as needed to have five evaluable participants for safety assessment. Patients with borderline resectable pancreatic adenocarcinoma will receive chemoradiation after completion of systemic chemotherapy prior to surgery. As per the standard of care, the time interval between completion of neoadjuvant chemotherapy and radiation will be 2-4 weeks for patients with borderline resectable pancreatic adenocarcinoma and the interval between completion of neoadjuvant treatment and surgery for all patients will be between 2-8 weeks.

We will compare experimental arm to the control arm to see if it has improved the major pathological response rate (MPR). The experimental treatment will be claimed to be successful if

$\Pr(p.e > p.c + 0.05 | \text{data}) > \theta_t$, where $p.e$ and $p.c$ are the MPR for the experimental arm and control arm, respectively, and θ_t is the threshold value. We assume the prior distributions $p.e \sim \text{Beta}(0.3, 0.7)$ and $p.c \sim \text{Beta}(0.13, 0.87)$, which reflect that the expected MPR being 30% in experimental arm and 13% in control arm.

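### The lead-in pause can end before the last lead-in patient's first on-treatment troponin I and NT-proBNP result, because none is scheduled before C3D1 and nothing requires that result

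*Combined protocol and SAP*

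**What the plan says.** **Enzyme schedule.** Section 10, footnote i, has cardiac enzymes checked at screening in all patients; they "thereafter will be checked on C3D1 and day 1 of every third cycle during treatment duration or as clinically indicated". Arm A also has a check when treatment ends. The calendar grid differs: its row for "Troponin I, NT proBNP" is marked at screening and in the column for day 1 of each chemotherapy cycle.

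**Lead-in.** Section 13.1, repeated in footnote D of the calendar: "Study will pause until the last patient accrued for safety lead-in has completed two full treatment cycles (i.e., 28 days". The first five evaluable Arm A patients form the lead-in. Neither place names the results that must be in hand when the pause ends.

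**Stopping rule.** Under 13.7.1, a Grade 3 or higher non-hematologic toxicity, with listed exceptions, is a DLT if at least possibly related to the investigational agent. Three or more DLTs in five patients stop the study. The DLT window there is 28 days counted from the end of drug administration.

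**Related cardiac provisions.** Section 7.1.1 lists cardiac toxicity among the NIS793 risks, and 6.2 sets graded actions for elevated enzymes. Footnote j says of cardiac imaging: "Thereafter it is repeated only if clinically indicated &/or if cardiac enzymes are elevated". EKGs are required on day 1 of each cycle for patients receiving NIS793. Section 2.2 states that NIS793 had not yet been given with FOLFIRINOX in a clinical trial.

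**The concern.** The lead-in is the first check on a new combination, and its go/no-go rule rests on five patients. A Grade 3 enzyme rise judged at least possibly related would, on a plain reading of 13.7.1, be a DLT. If it causes no symptoms, only a scheduled draw is likely to find it, and the first such draw falls nominally one day after the pause may end for the last patient. Accrual could then restart with that patient's enzyme status on treatment unknown. Repeat imaging depends partly on the enzymes, so a scheduled result could not prompt it earlier either.

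Two inconsistencies add to this. Sites following the grid would draw enzymes at C2D1, while sites following footnote i would not. The 28-day lead-in and the 13.7.1 window also give different answers on whether a day-29 finding belongs to the lead-in count.

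**Working it through.** **1. The plan's own boundary.** Prior Beta(0.33, 0.67), stop if Pr(p_tox > 0.33) > 0.7 (13.7.1). The posterior probability is 0.589 at 2/5 and 0.868 at 3/5, so the 3/5 boundary reproduces. Table 2 reproduces exactly with looks at 5, 10, 15, 20 and 25 patients (stopping probabilities 0.010, 0.093, 0.354, 0.710, 0.931). A single look at 5 does not reproduce it (0.009, 0.058, 0.163, 0.317, 0.500).

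**2. Timing for one patient.**
- The lead-in is 2 × 14 = 28 days; C3D1 = 1 + 2 × 14 = day 29.
- Dosing is on "day 1 of a 14-day cycle (+3/-1 days) for patients randomized to Arm A", so C3D1 may fall from 1 + 2 × 13 = day 27 to 1 + 2 × 17 = day 35.
- Section 5.2: "For all laboratory measures a window of up to 3 days prior to treatment day is acceptable". A sample for a nominal C3D1 may therefore be drawn from 29 − 3 = day 26. This is permitted, not required.
- Section 10: "Assessments must be performed prior to administration of any study agent". The C3D1 sample therefore reflects cycles 1 and 2.
- If the 13.7.1 window is counted from the C2D1 dose (day 15), it runs to about 15 + 28 = day 43. A day-29 value lies inside it, but the pause ends before it closes for the last patient.

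**3. How many patients have a C3D1 value when the pause ends.**
- Projected accrual is 45 patients in 36 months (13.2), or 1.25 per month. At 2:1 allocation, Arm A accrues 1.25 × 2/3 = 0.83 per month, a mean gap of about 37 days.
- Assume Poisson accrual at this rate and treatment starting at enrolment. The fourth patient is past C3D1 when the fifth completes day 28 if they started at least one day apart: exp(−1/36.5) = 0.97.
- The expected number of the first four past C3D1 is 3.97. If C3D1 or its result comes 3, 6 or 13 days late, it is 3.89, 3.81 or 3.62.

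**4. Effect on the 3/5 rule (illustration).** Assume a true DLT rate of 0.40, of which 0.10 is enzyme-only.
- Among four fully observed patients, P(X ≥ 3) = 4 × 0.4³ × 0.6 + 0.4⁴ = 0.179 and P(X = 2) = 6 × 0.4² × 0.6² = 0.346.
- P(≥ 3/5) = 0.179 + 0.346 × (observable rate in the fifth patient).

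| Enzyme results not counted | P(≥ 3/5) |
|---|---|
| None (fifth at 0.40) | 0.317 |
| Last patient only, enzyme-only rate 0.05 (fifth at 0.35) | 0.300 |
| Last patient only, enzyme-only rate 0.10 (fifth at 0.30) | 0.283 |
| All five, enzyme-only rate 0.10 (binomial, n = 5, p = 0.30) | 0.163 |

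**The case against.** A reader might infer that the lead-in decision is made with no scheduled enzyme data at all. The documents do not support that. The pause is tied to the last of five patients, not to each patient's own day 28, so with ordinary staggering the earlier patients will have passed C3D1. Screening values exist for everyone, and the laboratory window can bring even the fifth patient's sample inside 28 days.

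Nor do the documents support the inference that enzyme elevations cannot enter the 3/5 count. The C3D1 sample precedes dosing and so reflects cycles 1 and 2, and the 13.7.1 window can include it. A third tempting inference, that recorded cardiac events must rise from cycle 3 by construction, overlooks the EKGs, vital signs, examinations and adverse event assessments that start in cycle 1, and enzyme testing when clinically indicated.

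The other side can add that Table 2 implies later looks that would use later enzyme data, that the DSMB reviews toxicity twice a year, that footnote i applies by randomized arm (so stopping NIS793 alone does not cancel the C3D1 check), and that 7.1.1 puts NIS793 cardiac toxicity below 5 in 100.

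All of this stands and narrows the point, but does not remove it. Nothing enforces spacing between lead-in patients, the early draw is optional, an EKG is not an enzyme test, and later looks act only after more patients are exposed. If the lead-in period were read as each patient's own 28 days, a nominal day-29 value would fall outside it for all five. That reading conflicts with 13.7.1, which is why the two texts need reconciling.

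**Conclusion.** The point holds in a limited form. Footnote i schedules no enzyme test in cycles 1 and 2, and the end of the pause does not depend on any C3D1 result. At the projected accrual the gap mainly concerns the last lead-in patient; it widens if patients start almost together.

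Under the illustrative rates, missing the last patient costs 0.317 − 0.283 = 0.034 in the probability of reaching the boundary, or 0.317 − 0.300 = 0.017 at an enzyme-only rate of 0.05. The fall to 0.163 is a worst case in which all five results are left out. These sizes rest on an assumed 0.40 DLT rate and assumed enzyme-only rates, none given in the documents as expected values, and the four-of-five figure rests on Poisson accrual. It is a modest weakness in a go/no-go decision, and cheap to close.

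**What to change.** State in 13.1 and footnote D that the pause ends only once the already scheduled C3D1 troponin I and NT-proBNP results of the lead-in patients who reach C3 are available and counted in the 3/5 rule. No new draw is needed.

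Reconcile two pairs of passages:
- the calendar grid, marked for day 1 of each cycle, with footnote i;
- the 28-day lead-in in 13.1 and footnote D with the 13.7.1 DLT window, saying which period decides whether an event enters the lead-in count.

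The cost is wording in these places and a pause that may run a few days longer. If both cycles used the full +3 days, C3D1 would be day 35, which is 35 − 28 = 7 days after day 28, plus the time to obtain the result.
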